9.1.2 Serious Adverse Event

An SAE is defined as any untoward medical occurrence that at any dose:

- **Results in death** – The event must be the cause of death for the SAE to meet this serious criterion.
- **Is life-threatening** – The term “life-threatening” refers to an event in which the subject was at risk of death at the time of the event; it does not refer to an event that hypothetically might have caused death if it had been more severe.
- **Requires in-patient hospitalization or prolongation of existing hospitalization** – CSLB considers “hospitalization or prolongation of existing hospitalization” for at least 24 hours as the defining criterion for an SAE. Hospital admissions for planned surgery or

for normal disease management procedures (eg, chemotherapy) are not considered as defining criteria for SAEs.

- **Results in persistent or significant disability or incapacity.**
- **Is a congenital anomaly or birth defect.**
- **Is medically significant** – A medically significant event is defined as an event that does not necessarily meet any of the SAE criteria, but which is judged by a physician to potentially jeopardize the subject or require medical or surgical intervention to prevent one of the above outcomes listed as an SAE criterion.

Adverse events that do not fall into the above categories are defined as nonserious AEs.

9.1.3 Adverse Event of Special Interest

An AESI is an AE of scientific and medical concern specific to the sponsor's product or program, for which ongoing monitoring and rapid communication by the investigator to the sponsor is appropriate. Such an event might require further investigation in order to characterize and understand it. Depending on the nature of the event, rapid communication by the sponsor to other parties (eg, IDMC, regulators) might also be warranted.

The safety risk management plan of IgPro20 specifies the 'Important Identified Risks' and 'Important Potential Risks' for IgPro20. This involves systemic reactions reported to occur with IgPro20.

In this study, hemolysis, TEEs, and acute renal injury will be treated as AESIs.

All hemolysis events under the standardized MedDRA queries (SMQ) "hemolytic disorders, broad" will be considered AESI.

The following 3 narrow SMQs will be utilized for TEE evaluation:

- Embolic and thrombotic events, arterial
- Embolic and thrombotic events, venous
- Embolic and thrombotic events, vessel type unspecified and mixed arterial and venous

All acute renal injury events under SMQ “acute renal failure, narrow” will be considered AESIs.

9.1.4 Medical Device Incident

A medical device incident is any malfunction or deterioration in the characteristics and / or performance of a device as well as any inadequacy in the labeling or the instructions for use which, directly or indirectly, might lead to or might have led to the death of a subject / user / other person or to a serious deterioration in his / her state of health.

Note, not all medical device incidents lead to death or serious deterioration in health. The nonoccurrence of such a result might have been because of fortunate circumstances or to the intervention of health care personnel.

Examples of medical device incidents include:

- A subject, user, caregiver, or healthcare professional is injured as a result of a medical device failure or its misuse.
- A subject’s study intervention is interrupted or compromised by a medical device failure.

The reporting requirements for medical device incidents are detailed in [Section 9.6.3](#).

9.2 Intensity of Adverse Events

The intensity of each AE is to be assessed by the investigator as follows:

Severity	Definition
Mild	A type of AE that is usually transient and may require only minimal treatment or therapeutic intervention. The event does not generally interfere with usual activities of daily living.
Moderate	A type of AE that is usually alleviated with additional specific therapeutic intervention. The event interferes with usual activities of daily living, causing discomfort but poses no significant or permanent risk of harm to the subject.
Severe	A type of AE that interrupts usual activities of daily living, or significantly affects clinical status, or may require intensive therapeutic intervention.

9.3 Causality of Adverse Events

The causal relationship of an AE to IgPro20 or IgPro10 **must always be assessed** by the investigator. All AEs will be classified as either **related** or **not related** to IgPro20 or IgPro10.

If a causality assessment is not provided for an AE (including an SAE), that AE will be considered related to IgPro20 or IgPro10.

The degree of certainty with which an AE is attributed to IgPro20 or IgPro10 or an alternative cause (eg, natural history of the underlying disease, concomitant therapy) will be determined by how well the event can be understood in terms of:

- Known pharmacology of IgPro20 or IgPro10.
- Clinically and / or pathophysiologically plausible context.
- Reaction of a similar nature previously observed with similar products, or reported in the literature for similar products as being product related (eg, headache, facial flushing, pallor).
- Plausibility supported by the temporal relationship (eg, the event being related by time to administration or termination of treatment with IgPro20 or IgPro10, drug withdrawal or reproduced on rechallenge).

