3.3 Scientific Rationale

3.3.1 Study Design Rationale

The proposed crossover design with 2 sequences will provide a reliable estimate of IgPro20 relative bioavailability because IgPro20 and IgPro10 treatment differences are measured within a subject rather than between subjects with SSc; both inter- and intra-individual variability will be characterized. This study design will also help to investigate the potential difference in the relative bioavailability of IgPro20 (SCIG) when given before or after IgPro10 (IVIg) in SSc subjects. During both Treatment Period 1 and Treatment Period 2 in each sequence, several PK samples to measure IgG trough concentrations will be collected to assess the steady state of IgPro20 or IgPro10 and carry-over effects on Treatment Period 2 from Treatment Period 1. In addition, PK samples will be frequently collected over the last dose period to fully characterize the PK of IgPro20 and IgPro10, respectively, for each treatment period in this patient population. Specific PK assessments are described in [Section 8.1.2](#).

CCI

The 16 weeks of treatment for both IgPro20 and IgPro10 will allow for the assessment of safety and preliminary efficacy signals as well as assessment of IgPro20 and IgPro10 PK profiles at the steady state. The duration of PK assessments is based on IgG trough

concentrations measured in the pivotal phase 3 study in patients with CIDP (IgPro20_3003 study), indicating that IgPro20 and IgPro10 would reach steady state within approximately 8 weeks. Importantly, several trough concentrations will be determined for IgPro20 and IgPro10 in this study to confirm that steady state is reached before the full PK profile of IgPro20 or IgPro10 is assessed in subjects with SSc.

Not having a washout period between treatments will not impact the full PK characterization, since the full PK profile of IgPro10 in the respective treatment period of each sequence will be obtained at the end of the treatment period, when it is assumed that steady state will be reached. The relative bioavailability of IgPro20 will be evaluated based on the dose-normalized $AUC_{0-\tau}$ of IgPro20 and IgPro10 without the need of a washout interval. Moreover, no washout period between the 2 treatments will shorten the study duration and potentially be less burdensome for SSc subjects.

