8.1.1.2 Hemolysis Safety Assessment

Clinical hemolysis will be assessed at time points as detailed in the [Schedule of Assessments](#). The time windows for each assessment are detailed in [Table 2](#).

Criterion A

- Drop in hemoglobin of > 1 g/dL within a 28-day interval since the time of last administration of IgPro10 without clinical evidence of blood loss from gastrointestinal bleeding, menorrhagia, hemoptysis, major hematoma, or injury and not explained by repeated phlebotomy.

Criterion B

Presence of minor criteria documented within 28 days of last exposure to IgPro10, consisting of:

- Direct antiglobulin test (DAT) positive
- Haptoglobin $<$ lower limit of normal
- Lactate dehydrogenase $>$ upper limit of normal
- Total or indirect (unconjugated) bilirubin $>$ upper limit of normal or jaundiced
- Hemoglobinuria or red / dark urine
- Hemoglobinemia
- Spherocytosis
- Hepatosplenomegaly

Subjects fulfilling criterion A and at least 2 of the minor criteria of criterion B, where 1 of the minor criteria must be DAT positive, will be considered to have hemolysis.

If an AE of hemolysis is reported it should be graded by the investigator using this scale:

- Grade 1 – Laboratory evidence of hemolysis only (eg, direct antiglobulin test, schistocytes, decreased haptoglobin)
- Grade 2 – Clinical evidence of hemolysis and ≥ 2 g/dL decrease in hemoglobin
- Grade 3 – Transfusion or medical intervention indicated (eg, steroids)
- Grade 4 – Life-threatening consequences; urgent intervention indicated
- Grade 5 – Death

Subjects with hemolysis Grade 3 and above will be assessed by an investigator or medically qualified designee whether it is in the best interest of the subject to continue the study and safe to continue the investigational treatment.

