8.1 Missing Data

8.1.1 Imputation of Non-Date Missing Data

Missing data occurs when any requested data is not provided, leading to blank fields on the collection instrument. These data will be indicated by the use of a “blank” in subject listing displays. Answers such as “Not applicable” and “Not evaluable” are not considered to be missing data and should be displayed as such.

Subjects with the designation of treatment relationship for AEs and SAEs missing will have the worst case assumed to impute the relationship: if relationship to study treatment is missing it will be assumed to be “Yes”. There will be no other imputation for missing data other than as described in Section 8.1.2 for partial dates and times.

In the event that the study is terminated, all available data will be listed and a review carried out by the study team to assess which statistical analyses are to be performed.

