8.3 Study Periods Relative to Treatment

Definitions of the endpoint assessment and definition of start and end of study periods are presented in [Table 1](#) and [Table 2](#).

Table 1: Timing of Endpoint and Reference Assessments

	Definition	Start of Assessment Period	End of Assessment Period
By Treatment	1 IgPro20 Treatment Sequence A/ Treatment Period 1 and Treatment Sequence B/ Treatment Period 2	Week 1 Week 17	Week 17 ¹ Week 32
	2 IgPro10 Treatment Sequence A/ Treatment Period 2 and Treatment Sequence B/ Treatment Period 1	Week 17 Week 1	Week 32 Week 17 ²
By Treatment Sequence	1 Treatment Sequence A	Week 1	Week 32
	2 Treatment Sequence B	Week 1	Week 32
By Treatment and Treatment Period	1 IgPro20 in Treatment Period 1 Treatment Sequence A	Week 1	Week 17 ¹
	2 IgPro10 in Treatment Period 1 Treatment Sequence B	Week 1	Week 17 ²
	3 IgPro10 in Treatment Period 2 Treatment Sequence A	Week 17	Week 32
	4 IgPro20 in Treatment Period 2 Treatment Sequence B	Week 17	Week 32
Overall	1 Both Treatment Sequences, all Treatment Periods Treatment Sequence A/ Treatment Period 1, Treatment Sequence B/ Treatment Period 1, Treatment Sequence A/ Treatment Period 2, Treatment Sequence B/ Treatment Period 2	Week 1 Week 17	Week 17 Week 32

¹ Before first infusion of IgPro10.² Before first infusion of IgPro20.

Table 2: Treatment Periods

Treatment Sequence/ Treatment Period	Treatment	Start of Treatment Period	End of Treatment Period
Treatment Sequence A/ Treatment Period 1	IgPro20	Start date and time of the first IgPro20 Infusion	Start date and time of the first IgPro10 Infusion or EOS, if there is no IgPro10 Infusion
Treatment Sequence A/ Treatment Period 2	IgPro10	Start date and time of the first IgPro10 Infusion	EOS
Treatment Sequence B/ Treatment Period 1	IgPro10	Start date and time of the first IgPro10 Infusion	Start date and time of the first IgPro20 Infusion or EOS, if there is no IgPro20 Infusion
Treatment Sequence B/ Treatment Period 2	IgPro20	Start date and time of the first IgPro20 Infusion	EOS

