8.3.1 Study Periods for Adverse Events

AEs with onset date/ time at or after start of first infusion of study treatment are TEAEs. If the time of onset of an AE is missing: AEs with onset date at or after start of first infusion of study treatment are TEAEs. Assessment whether an AE is considered treatment-emergent, will take place after imputation of partially missing dates (see [Section 8.1.2](#)).

The TEAE analysis will be done for the study periods and groups shown in [Section 11](#). An AE will be counted for the analysis of a study period if the onset of the event falls within the study period. For the definition of start and end of the study periods see [Table 2](#).

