11.2 Adverse Events

All AEs will be coded by the Medical Dictionary for Regulatory Activities. System organ class (SOC), high-level group term (HLGT), high-level term (HLT), preferred term (PT), and lower-level term (LLT) will be provided in the AE dataset.

Summaries will be presented for the following combinations of Treatment Sequence and Treatment Period (respective Treatment Sequences [A/B] and Treatment Periods [1/2] are given in parentheses):

- IgPro20 (A/1 and B/2)
- IgPro10 (A/2 and B/1)
- IgPro20/ Treatment Period 1 (A/1)
- IgPro20/ Treatment Period 2 (B/2)
- IgPro10/ Treatment Period 1 (B/1)
- IgPro10/ Treatment Period 2 (A/2)
- Total (A/1, A/2, B/1, and B/2)

Infusion site reactions (ISR) comprise all AEs reported within the MedDRA HLTs “Administration site reactions NEC” or “Infusion site reactions”.

Summaries of AEs created to assess the COVID-19 impact are described in Section 7.4.

Refer to Section 11.3 for the definition of Adverse Events of Special Interest (AESIs).

- An overview summary of TEAEs, including number of subjects, percentages of subjects, and the number of events by Treatment Sequence, treatment, and Treatment Period including the following:
 - Any TEAE
 - Any serious TEAE
 - TEAEs leading to interruption of IP
 - TEAEs leading to permanent discontinuation of IP
 - TEAEs leading to withdrawal from study
 - Temporally associated TEAEs
 - Treatment-emergent AESIs (Hemolysis, TEE, Acute Renal Injury)
 - Any serious treatment-emergent AESIs
 - Treatment-emergent AESIs leading to permanent discontinuation of IP
 - Treatment-emergent AESIs leading to withdrawal from study

- Related treatment-emergent AESIs
 - Treatment-emergent AESIs by Grade
 - Treatment-emergent AESIs Grade 3 and above
 - TEAEs by causality (related to IP)
 - TEAEs by severity (mild, moderate, severe)
 - TEAEs by outcome (“recovered or resolved” vs. all other outcomes combined)
 - Any ISR
 - ISRs leading to interruption of IP
 - ISRs leading to permanent discontinuation of IP
 - ISRs leading to withdrawal from study
 - ISRs by causality (related to IP)
 - ISRs by severity (mild, moderate, severe)
 - ISRs by outcome (“recovered or resolved” vs. all other outcomes combined)
- The following descriptive tables will be generated for TEAEs, including number of subjects, percentages of subjects, and the number of events:
 - TEAEs by SOC and PT
 - TEAEs by PT
 - TEAEs by SOC, PT, and maximum severity (without number of events)

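### Causality is one judgement across both products and the product is assigned by onset alone, so a first-product reaction that starts after the switch is tabulated as related to the second product (few events expected)

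*Protocol*

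**What the plan says.** **Causality.** Protocol 9.3: "All AEs will be classified as either related or not related to IgPro20 or IgPro10". If no judgement is given, "that AE will be considered related to IgPro20 or IgPro10". SAP 8.1.1 handles the same variable in the singular: "if relationship to study treatment is missing it will be assumed to be" Yes. The overview table in SAP 11.2 has the row "TEAEs by causality (related to IP"), and the same section lists related-event tables by system organ class and preferred term and for events of special interest. None of these names a product in the causality judgement.

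**Product.** SAP 8.3.1: "An AE will be counted for the analysis of a study period if the onset of the event falls within the study period". SAP Table 2 sets the boundary. In Sequence A, Period 1 ends at "Start date and time of the first IgPro10 Infusion or EOS, if there is no IgPro10 Infusion"; Sequence B mirrors this. SAP 11.2 then presents events for each product in each period, for each product pooled over periods, and in total.

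**Washout.** Protocol 3.3.1: "Not having a washout period between treatments will not impact the full PK characterization". The reasons given are pharmacokinetics, study duration and subject burden. The section expects to examine carry-over through trough levels, but does not discuss attribution of adverse events.

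**Endpoint.** Protocol 2.1.2 makes adverse events by causality, summarised by treatment, part of the primary endpoint for IgPro20. Protocol 2.2.2 does the same for IgPro10 as a secondary endpoint.

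**The concern.** In a crossover, a related event needs two pieces of information: that the investigator thinks a product caused it, and which product. The plan records the first and infers the second from the calendar. The inference fails for an event that starts after the first infusion of the second product but that the investigator attributes to the first. It enters the second product's column as related, and nothing in the SAP moves it back.

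The documents supply one example. The minor hemolysis criteria in Protocol 8.1.1.2 are those "documented within 28 days of last exposure to IgPro10", and the hemoglobin criterion uses the same 28-day interval. In Sequence B that interval can end after IgPro20 has begun. An event could thus meet the protocol's own definition of hemolysis following IgPro10 and still be tabulated under IgPro20. At stake is the causality part of the safety profile of IgPro20, the product the trial was set up to assess.

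**Working it through.** **1. The plan's own figure, which fixes the last IgPro20 week.** Protocol 10.1 states 28 IgPro20 infusions per subject and 560 in total. The SAP glossary gives 14 weekly infusions per IgPro20 period, each of two sessions. 14 × 2 = 28 and 28 × 20 = 560, so the figure is reproduced. In Sequence A the last IgPro20 week is Week 14.

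**2. Infusion-free gap before the switch.** Study day = (week − 1) × 7 + day of week.

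- First Period 2 infusion, Week 17 Day 1: 16 × 7 + 1 = day 113.
- Sequence A, last IgPro20 session, Week 14 Day 3 or 4 (Protocol 3.2.1): 13 × 7 + 3 = 94, or 95. Gap = 113 − 94 = 19, or 18 days.
- Sequence B, last IgPro10 infusion day, Week 13 Day 2 to 5 (Protocol 3.2.2): 12 × 7 + 2 = 86, to 89. Gap = 113 − 86 = 27, to 24 days.

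The ±2-day window at both visits can shift each gap by up to 4 days: 14 to 23 days in Sequence A, 20 to 31 in Sequence B. Table 2 assigns events in the gap to Period 1, which is correct.

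**3. How far a 28-day window passes the switch.**

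| Sequence | Last Period 1 dose (day) | +28 days | Days past day 113 |
|---|---|---|---|
| A (after IgPro20) | 94 to 95 | 122 to 123 | 9 to 10 |
| B (after IgPro10) | 86 to 89 | 114 to 117 | 1 to 4 |

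The hemolysis window applies after IgPro10, so Sequence B is the relevant row. The Sequence A row only shows what a 28-day flag would reach there.

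**4. Hemolysis sampling around the Sequence B switch.** Samples are scheduled at Week 15 (Protocol 8.6.5.4), at Week 17 before infusion (8.6.6.1), and then at end of treatment. No scheduled sample falls in the 1 to 4 days after the switch. Only an event found clinically or at an unscheduled visit could be misassigned there.

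**5. Columns affected.** A late first-product reaction reaches the Period 2 column of the second product and the pooled column for that product. IgPro20/Period 1 and IgPro10/Period 1 are tabulated separately in SAP 11.2 and have no earlier product to carry over.

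**6. Size of one misassignment.** With 20 evaluable subjects, 1/20 = 5.0 percentage points of a pooled column. If the safety set reaches the 26 planned for randomization, 1/26 = 3.8 points. This assumes the subject has no other related event in the same row.

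**The case against.** The strongest objection is that this will almost never matter.

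- **Latency.** The latencies the documents do state are short: several hours to 2 days for aseptic meningitis and 1 to 6 hours for transfusion-related acute lung injury (Protocol 7.1), and a 72-hour window for temporal association (SAP 11.2). All are far inside an 18-day gap. No long latency is stated for IgPro20, and none for thrombosis.
- **Visibility.** The SAP derives time to onset from the last infusion and from the start of the period (8.2.3). It lists all adverse events, and its listings carry sequence and period. In a trial this small a reader can find early Period 2 related events by hand.
- **Separability.** Protocol 1.2.2 says the two products contain the same purified IgG drug substance. For systemic effects of circulating IgG, an investigator may have little basis for naming one.
- **Unseen eCRF.** The wording of Protocol 9.3 could be read product by product, and the eCRF and table shells are not among the documents.

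Most of this stands as a limit on size. It does not supply the missing rule. The listings permit a manual check, but the related-event tables would still carry the wrong product. If the eCRF has a product-specific field, the SAP does not use it.

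A reader might go further and infer, from the absence of washout, that the early weeks of Period 2 are generally contaminated and that delayed thrombosis or hemolysis is systematically charged to IgPro20. The documents do not support that. They give no IgG half-life, and residual IgG is not itself a delayed reaction. The schedule also contains a substantial infusion-free gap although no washout is planned.

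**Conclusion.** The gap in the rules is real and its expected effect is small. With one causality flag and onset-only assignment, any reaction judged due to the first product but starting after the switch is reported as related to the second, and no section corrects this. The effect is confined to the related-event rows of the Period 2 and pooled by-treatment columns. At about 4 to 5 points per misassigned subject in a pooled column, one event would be noticeable, but few are expected.

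The documents support neither an expected count nor the claim that such events will occur in both sequences. The only late-reaction window they give is the 28-day one after IgPro10, which is relevant in Sequence B.

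The conclusion rests on three assumptions: the single relationship variable in the SAP reflects how the eCRF collects causality; the gaps follow the visit schedule, with IgPro20 infusions in 14 of the 16 weeks; and visits occur on their nominal days.

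**What to change.** **Preferred.** For adverse events with onset in Period 2, record the relationship to IgPro20 and to IgPro10 separately, allowing either, both or neither. Build each product's related-event tables from the judgement on that product. State in the SAP how a missing answer on one product is imputed.

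**If the eCRF cannot change.** Before database lock, derive a flag for related events with onset after the switch and within a prespecified lag of the last Period 1 dose. Show the by-product related counts with and without flagged events as a sensitivity row. A 28-day lag matches the protocol's hemolysis window, but its reach is limited: 9 to 10 days into Period 2 in Sequence A and 1 to 4 days in Sequence B on the nominal schedule.

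**Cost.** One extra field, or one derived flag and one table row. The onset-based tables of treatment-emergent events stay as they are, and dosing, schedule and clinical management are not touched. The drawback is that investigators may often be unable to separate two products with the same drug substance. The answer may then be both, which would at least show the uncertainty in the tables.
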